5.2. Subject Distribution

Summarize enrollment and completion numbers by center, listing dropout cases. Provide comparisons of dataset sizes across groups, case distribution by center, overall dropout rates, and detailed reasons for non-completion.

5.3. Demographic and Baseline Characteristics Analysis

Describe patient demographics (age, gender, etc.), relevant medical history, and treatment history. Compare characteristics such as age and gender between groups to assess comparability. Demographic analysis is based on the FAS analysis set.

5.4. Efficacy Analysis

5.4.1. Primary Efficacy

Primary efficacy evaluation is based on the Full Analysis Set (FAS) and the Per-Protocol Set (PPS).

This trial employs a prospective, multicenter, randomized controlled design with a non-inferiority comparison. It demonstrates that the investigational device meets clinical application requirements by comparing it with an approved comparator. The primary endpoint evaluates intraoperative vascular recanalization success rate, with the corresponding statistical hypothesis test defined as:

$$H_0 : p_T - p_C \leq -\Delta$$

$$H_1 : p_T - p_C > -\Delta$$

In the formula, P_T represents the expected recanalization success rate in the test group, P_C denotes the expected recanalization success rate in the control group, and $-\Delta$ indicates the non-inferiority margin of -12.5%.

The target vessel recanalization rates between the test and control groups will be compared, and the 95% confidence interval (CI) for the rate difference between the two groups will be calculated. If the lower limit of the 95% CI for the rate difference is greater than -12.5%, the test group will be considered non-inferior to the control group. The intergroup comparison will employ a CMH chi-square analysis adjusted for center effects.

5.4.2. Secondary Endpoints

Secondary efficacy assessments were based on the full analysis set (FAS) and the per-protocol set (PPS).

The 90-day postoperative mRS 0-2 rate, the proportion of subjects with NIHSS improvement >4 points, and the device procedural success rate were analyzed as categorical data; recanalization time was analyzed as a quantitative endpoint.

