3.2. Contents

The study is a prospective, multicenter, randomized controlled, non-inferiority clinical trial, of which the investigational device is Sinomed Neurovita Ghunter Revascularization Device and the control device is Solitaire FR (hereinafter referred to as the control product under the trade name Solitaire FR) distributed by Covidien Healthcare International Trading (Shanghai) Co., Ltd.; the study is planned to be conducted in more than 10 sites and include 220 subjects. The subjects who meet the inclusion criteria will be randomized into the test group or control group in 1:1. The study is to collect and evaluate whether the success rate of instant recanalization is not inferior to Solitaire FR when Sinomed Neurovita Ghunter Revascularization Device is used for endovascular treatment of acute ischemic stroke, and to evaluate whether there is a statistically significant difference in the proportion of subjects with mRS score of 0 - 2 on 90d postoperatively, the time from femoral artery puncture to recanalization/the end time of operation for subjects whose recanalization failed, the proportion of subjects with NIHSS score decrease > 4 , and the success rate of device operation as compared with Solitaire FR when Ghunter Revascularization Device is used for endovascular treatment of acute ischemic stroke. Also, whether there is statistical difference in incidence of symptomatic intracranial hemorrhage within 24h postoperatively, all-cause mortality within 90d, incidence of SAE, incidence of AE, and incidence of device defects between Ghunter Revascularization Device and Solitaire FR for endovascular treatment of acute ischemic stroke will be evaluated.

4. Background of Clinical Trial

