7.1.2.3. Primary Efficacy Indicator

For the primary endpoint of recanalization success rate, at the level of $\alpha = 0.025$ (one-sided test) and $\beta = 0.2$, the success rate of target vessel recanalization in the study and control groups are compared, respectively. The 95% CI for their difference is calculated. If the lower limit of 95% CI for their difference is greater than -12.5%, it is considered that the test group is non-inferior to the control group. The inter-group comparison will be performed using the center effect-modified CMH chi-squared analysis, and the Logistics regression model can be considered for the inter-group comparison as appropriate to correct for the effects

of factors such as the center.

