7.1.2.4. Secondary Efficacy Indicators

The secondary efficacy evaluation is based on Full Analysis Set (FAS) and Per-Protocol Set (PPS). For the statistical description and inference of the data, the applicable descriptive indicators and hypothesis test methods are selected based on the characteristics of the data.

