5.1. General Principles

Statistical analyses were performed using SAS version 9.4 statistical software.

Descriptive Statistics: Count data were described using frequency and proportion; continuous data were described using mean, standard deviation, maximum, minimum, median, and 25th and 75th percentiles.

Statistical Inference: For comparisons between two groups, quantitative indicators were analyzed using paired t-tests or Wilcoxon signed-rank tests based on data distribution. Categorical indicators were analyzed using chi-square tests or exact probability methods (if chi-square tests were not applicable). Ordinal data were analyzed using Wilcoxon signed-rank tests or the Cumulative

Hypothesis Test (CMH).

Unless otherwise specified, all statistical tests were two-tailed. A P-value < 0.05 (two-tailed) was considered statistically significant.

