6.6.3. Secondary efficacy endpoint

Table29 mRS 0-2 at 90 days post-surgery

Item	Indicator	FAS		PPS	
		Experimental Group	Control Group	Experimental Group	Control Group
mRS 0-2 at 90 days post-surgery	Yes n(%)				
	No n(%)				
	Total (Missing)				
	Statistic (CMH)				
	P-value				
90-day postoperative mRS	Grade 0 n(%)				
	Grade 1 n(%)				
	Grade 2 n(%)				
	Grade 3 n(%)				

Item	Indicator	FAS		PPS	
		Experimental Group	Control Group	Experimental Group	Control Group
	Grade 4 n(%)				
	Level 5 n(%)				
	Level 6 n(%)				
	Total (Missing)				
	Statistic				
	P-value				

Table30 Recanalization Time

Item	Indicator	FAS		PPS	
		Experimental Group	Control Group	Experimental Group	Control Group
Recanalization Time (min)	N(Missing)				
	Mean(SD)				
	Median				
	Q1, Q3				
	Min, Max				
	Statistic				
	P-value				

Note: Time to reperfusion = End time - Femoral artery puncture time (If reperfusion is successful, the end time is the time of successful reperfusion; if reperfusion fails, the end time is recorded as the time of surgical completion).

Table31 Postoperative NIHSS Score Improvement

Item	Indicator	FAS		PPS	
		Experimental Group	Control Group	Experimental Group	Control Group
Preoperative NIHSS Score	N(Missing)				
	Mean(SD)				
	Median				
	Q1, Q3				
	Min,Max				
	Statistic				
	P-value				
NIHSS score at 24±12 hours postoperatively	N(Missing)				
	Mean(SD)				
	Median				
	Q1, Q3				
	Min,Max				
	Statistic				
	P-value				

Item	Indicator	FAS		PPS	
		Experimental Group	Control Group	Experimental Group	Control Group
NIHSS score reduction >4 points (postoperative 24±12 h vs. preoperative)	Yes n(%)				
	No n(%)				
	Total (Missing)				
	Statistic				
NIHSS score at 7±2 days post-op/prior to discharge	P-value				
	N(Missing)				
	Mean (SD)				
	Median				
	Q1, Q3				
	Min,Max				
	Statistic				
Proportion of subjects with NIHSS score reduction >4 points (7 ± 2 days post-op/prior to discharge)	P-value				
	Yes n(%)				
	No n(%)				
	Total (Missing)				
	Statistic				
	P-value				

Table32 Device Operation Success Rate (per device unit)

Item	Indicator	FAS	PPS
Whether Device Operation Was Successful	Yes n(%)		
	No n(%)		
	Total (Missing)		

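### The 90-day mRS 0-2 and NIHSS responder comparisons are not adjusted for preoperative NIHSS or age, although both are collected; adjusting would be a modest efficiency gain and does not correct an error

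*SAP*

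**What the plan says.** Protocol 3.2 sets out "to evaluate whether there is a statistically significant difference in the proportion of subjects with mRS score of 0 - 2 on 90d postoperatively", and names the proportion with NIHSS decrease >4 among the other endpoints to be compared in the same way.

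For method, Protocol 7.1.2.4 says only that "hypothesis test methods are selected based on the characteristics of the data". SAP 5.4.2 puts the mRS 0-2 rate and the NIHSS >4 rate at the head of a sentence that ends "the device procedural success rate were analyzed as categorical data". SAP 5.1 gives the test for such data: "Categorical indicators were analyzed using chi-square tests or exact probability methods (if chi-square tests were not applicable"). In the table shells, Table 29 labels the mRS 0-2 row "Statistic (CMH") and names no stratum. Table 31 has only an unspecified statistic and a P-value for the NIHSS responder rows.

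Adjustment appears only for the primary endpoint. In SAP 5.4.1, "The intergroup comparison will employ a CMH chi-square analysis adjusted for center effects". In Protocol 7.1.2.3, "the Logistics regression model can be considered for the inter-group comparison as appropriate", to correct for factors such as centre.

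The baseline variables are already in the data. Table 31 summarises the "Preoperative NIHSS Score" as a continuous variable, Table 4 has age, and Table 5 has onset window. SAP 5.3 uses age to judge comparability of the groups. No secondary comparison uses any of the three as a covariate.

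**The concern.** These two endpoints are the trial's effectiveness measures of neurological and functional outcome; the others (recanalization, procedure time, device operation) are procedural. With 110 subjects per arm, a comparison of two proportions is imprecise. Protocol 6.1.2 describes block randomisation through a web system and mentions no stratification by severity, so chance differences in baseline severity are possible.

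For the NIHSS endpoint the link to baseline needs no outside evidence. A subject's chance of responding depends on where that subject starts, and the planned test ignores this. What is at stake is precision that the collected data could supply, and some protection against chance imbalance.

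**Working it through.** **The plan's own figure.** The only sample size calculation concerns the primary endpoint (Protocol 7.2.1, SAP 1.5): 89% in both groups, margin 12.5%, one-sided alpha 0.025, power 80%.

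n = (1.960 + 0.842)² × (2 × 0.89 × 0.11) / 0.125² = 98.36, rounded up to 99; 99 / 0.90 = 110 per group.

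This reproduces the plan and is unaffected by the present point. The documents give no expected rate, power or precision for either responder endpoint.

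**NIHSS response and baseline.** Entry requires NIHSS of at least 6 (Protocol 6.1.5.1). Response requires a decrease >4 (Protocol 6.1.6, SAP 2.1.2), that is, at least 5 points. A subject entering at 6 must reach 1 or less, a loss of 5/6 of the score. A subject entering at 20 need only reach 15, a loss of 5/20.

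**Chance imbalance.** With an assumed NIHSS SD of 6, the 95% range for the difference in arm means is ±1.96 × 6 × √(2/110) = ±1.6 points.

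**Precision by formula.** The unadjusted SE of a risk difference is √(2p(1−p)/n). With an assumed p = 0.50 and n = 110, SE = 0.0674 and the 95% half-width is 13.2 points. A standardised, covariate-adjusted risk difference has SE of about SE × √(1−R²), where R² is the share of outcome variance that the covariates explain.

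| Assumed R² | Half-width (points) | Effective n per arm, 110/(1−R²) |
|---|---|---|
| 0 | 13.2 | 110 |
| 0.05 | 12.9 | 116 |
| 0.10 | 12.5 | 122 |
| 0.20 | 11.8 | 138 |
| 0.30 | 11.1 | 157 |

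A simulation of logistic regression with standardisation (3,000 trials, 110 per arm, baseline NIHSS and age as covariates) gave adjusted/unadjusted variance of 0.99, 0.91 and 0.84 at R² of about 0.02, 0.10 and 0.19. The formula is a fair guide, and the gain is about 1% of variance at the weak end.

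**Precision by assumed AUC, mRS 0-2 only.** Inputs are 110 per arm, 45% control rate, log odds ratio 0.7, NIHSS SD 6 and age SD 12, all assumed. Entries are unadjusted/adjusted variance.

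| AUC of NIHSS and age | 1,500 trials | 1,500 trials, repeat | 3,000 trials |
|---|---|---|---|
| about 0.64 (0.63 in the repeat) | 1.03 | 1.05 | 1.05 |
| 0.70 | 1.13 | 1.17 | 1.13 |
| 0.76 | 1.24 | 1.31 | 1.20 |

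The CI shortens by 1 − 1/√1.03 = 1.5% at the low end and 1 − 1/√1.31 = 12.6% at the high end. In subjects, this is worth 220 × 0.03 = 7 to 220 × 0.31 = 68 more.

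**Type I error with no treatment effect.** Unadjusted 4.9% to 5.2%. Adjusted 4.7% to 5.3% in one set of runs and 4.5% to 5.5% in another. Both methods hold the 5% level within simulation error.

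The AUC runs assume complete data on 110 per arm, although the plan allows up to 10% dropout and SAP 4 does not impute secondary endpoints. Onset window was not in any simulated model, and the NIHSS responder endpoint was not simulated.

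**The case against.** The strongest reply is that nothing here is wrong. The unadjusted comparison is valid under randomisation, its type I error is held, neither endpoint enters the pass/fail rule (Protocol 8.2), and no power is promised for either. That stands.

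Several stronger readings are tempting, and the documents do not support them.

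- A reader might infer that the mRS 0-2 test is settled as a plain chi-square. Table 29 says CMH. That could mean stratification by centre, as in SAP 5.4.1, or an unstratified CMH that is in effect a chi-square; Tables 7 and 13 put the same label on yes/no baseline items. Neither reading adjusts for NIHSS or age.
- A reader might infer that severity, age and onset window are known to predict 90-day mRS strongly. The documents give no such figure. Only the link between NIHSS response and its own baseline follows from them.
- A reader might infer that the plan's intervals are too wide. Tables 29 and 31 plan only a statistic and P-value, with no between-group interval. The gain shows in the interval that should be added.
- A reader might infer a gain in power. The simulated odds ratio implies a test-arm rate of about 59% to 61%, a superiority of some 14 to 16 points on mRS. That fits poorly with a trial that assumes equal recanalization of 89% in both arms, so interval width is the better measure.

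A further caution is that a conditional odds ratio from a logistic model is a different estimand, and its SE need not shrink. The precision argument applies to the standardised risk difference.

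**Conclusion.** The plan leaves both responder comparisons unadjusted for preoperative NIHSS and age, which are already collected. This is a missed efficiency of low severity. It does not threaten the validity of the secondary tests and has no bearing on the non-inferiority conclusion.

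For mRS 0-2 the gain is modest: a variance factor of about 1.03 to 1.3, or a 95% CI about 2% to 13% shorter, for an assumed AUC of about 0.64 to 0.76. With weak covariates it is near nil. The responder rate, treatment effect, covariate SDs and prognostic strength behind these figures are all assumptions. For the NIHSS responder endpoint the dependence on baseline is certain, but the gain has no figure.

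**What to change.** Before database lock, amend SAP 5.4.2 as follows.

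1. For mRS 0-2 at 90 days, and for NIHSS decrease >4 at each of the two time points in Table 31, fit a logistic model with arm, continuous preoperative NIHSS, age and onset window (0-6 h, 6-24 h). Fix the covariates and their functional form in advance.
2. Report the result as a standardised (marginal) risk difference with 95% CI. State how the standard error is obtained, and what is done if the model does not converge.
3. Keep the planned unadjusted or CMH test as supportive.
4. State the CMH stratum in Table 29, and add the difference and its interval to Tables 29 and 31.

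Protocol 7.1.2.4 leaves the method open, and Protocol 8.5 allows recorded changes before the SAP is final, so this fits the existing rules. If the database is already locked, label the adjusted results exploratory. The cost is a few lines of SAP text and SAS code. No new data are needed.

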5.5. Safety Analysis

The incidence of symptomatic intracranial hemorrhage within 24 hours postoperatively (data from the central reading center) and all-cause mortality within 90 days postoperatively were analyzed as categorical data.

Adverse events were described by the number of cases and incidence rate, with detailed descriptions of the specific manifestations, severity, and relationship to the study product for all adverse events that occurred.

The number and proportion of cases with normal findings before treatment and abnormal findings after treatment were described separately.

Device defects were described using incidence rates.

6. Statistical Analysis Results

6.1. Subject Distribution

Table1 Case distribution across centers

Center ID	Research Center	Group	Number			
			EnrollmentCount	Dropout Rate (%)	Dropout of ExclusionsRate (%)	Completed
01		Experimental group				
		Control Group				
		Total				
02		Experimental Group				
		Control Group				
		Total				
03		Experimental Group				
		Control Group				
		Total				
.....		Experimental Group				
		Control Group				
		Total				
Total		Experimental Group				
		Control Group				
		Total				

Note 1: Number of completers = Number enrolled - Number of dropouts.

Note 2: Exclusion refers to subjects who completed the trial but were not included in the PPS set.

Table2 Population Distribution by Center

Research Hospital	FAS		PPS		SS		Total
	Center	Experimental group	Control group	Experimental group	Control Group	Experimental group	
01							
02							
03							
.....							
Total							

Table3 Enrolled Cases and Safety/Efficacy Analysis Dataset

Item	Indicator	Experimental Group	Control Group	Total
Reasons for Randomly Assigned				
Early Withdrawal	Completed Trial			
	Adverse events			
	Unsatisfactory treatment response			
	Subject withdrawal of informed consent			
	Protocol violation			
	Other			
	Subject or family member requests withdrawal from the study			
	Loss to follow-up			
	Death			
	Total			
FAS				
PPS				
SS				

6.2. Demographic and Baseline Characteristics (FAS)

6.2.1. Demographic Information

Table4 Population Demographic Information

Project	Indicator	Experimental Group	Control Group	Total
Gender	Male n(%)			
	Female n(%)			
	Total (Missing)			
	Statistic			
	P-value			
Age (years)	N(Missing)			
	Mean (SD)			
	Median			
	Q1, Q3			
	Min, Max			
	Statistic			
	P-value			
Height (cm)	N(Missing)			
	Mean(SD)			
	Median			

Project	Indicator	Experimental Group	Control Group	Total
Weight (kg)	Q1, Q3			
	Min, Max			
	Statistic			
	P-value			
	N(Missing)			
	Mean(SD)			
	Median			
	Q1, Q3			
	Min,Max			
	Statistic			
	P-value			

Note: Age = (Date of informed consent signature - Date of birth) / 365.25, rounded down.

6.2.2. Personal and Medical History

Table5 Clinical Diagnosis

Item	Indicator	Experimental Group	Control Group	Total
Acute	Yes n(%)			
Ischemic	No n(%)			
Stroke	Total (Missing)			
	Statistic			
	P-value			
Onset time	0-6 hours n(%)			
	6-24h n(%)			
	>24h n(%)			
	Total (Missing)			
	Statistic			
	P-value			
Other	None n(%)			
comorbidities	Yes n(%)			
or admission	Total (Missing)			
diagnoses	Statistic			
	P-value			

Table6 Past Medical History

Item	Indicator	Experimental Group	Control Group	Total
Hypertension	Yes n(%)			
	No n(%)			
	Unknown n(%)			
	Total (Missing)			

Item	Indicator	Experimental Group	Control Group	Total
Diabetes	Statistic			
	P-value			
	Yes n(%)			
	No n(%)			
	Unknown n(%)			
	Total (Missing)			
Hyperlipidemia	Statistic			
	P-value			
	Yes n(%)			
	No n(%)			
	Unknown n(%)			
	Total (Missing)			
Atrial fibrillation	Statistic			
	P-value			
	Yes n(%)			
	No n(%)			
	Unknown n(%)			
	Total (Missing)			
Coronary heart disease	Statistic			
	P-value			
	Yes n(%)			
	No n(%)			
	Unknown n(%)			
	Total (Missing)			
Hyperhomocysteinemia	Statistic			
	P-value			
	Yes n(%)			
	No n(%)			
	Unknown n(%)			
	Total (Missing)			
Heart failure	Statistic			
	P-value			
	Yes n(%)			
	No n(%)			
	Unknown n(%)			
	Total (Missing)			
Recent smoking (within 6 months)	Statistic			
	P-value			
	Yes n(%)			
	No n(%)			
	Unknown n(%)			

Item	Indicator	Experimental Group	Control Group	Total
Previous smoking (6 months prior)	Total (Missing)			
	Statistic			
	P-value			
	Yes n(%)			
	No n(%)			
	Unknown n(%)			
	Total (Missing)			
	Statistic			
	P-value			
History of Alcohol Consumption	Yes n(%)			
	No n(%)			
	Unknown n(%)			
	Total (Missing)			
	Statistic			
	P-value			
History of combined peripheral arterial stenosis ($\geq 50\%$) or occlusion	Yes n(%)			
	No n(%)			
	Unknown n(%)			
	Total (Missing)			
	Statistical measure			
	P-value			
History of stroke	Yes n(%)			
	No n(%)			
	Unknown n(%)			
	Total (Missing)			
	Statistical measure			
	P-value			
Previous Stroke Type	Ischemic n(%)			
	Hemorrhagic n(%)			
	Mixed n(%)			
	Total (Missing)			
	Statistical Measure			
	P-value			
Liver failure	Yes n(%)			
	No n(%)			
	Unknown n(%)			
	Total (Missing)			
	Statistic			
	P-value			
Renal failure	Yes n(%)			
	No n(%)			

Item	Indicator	Experimental Group	Control Group	Total
	Unknown n(%)			
	Total (Missing)			
	Statistic			
	P-value			

Table7 Clinical Score

Item	Indicator	Experimental Group	Control Group	Total
mRS score <2 before onset	Yes n(%)			
	No n(%)			
	Total (Missing)			
	Statistic (CMH)			
	P-value			
NIHSS score \geq 6 before enrollment	Yes n(%)			
	No n(%)			
	Total (Missing)			
	Statistic (CMH)			
	P-value			

Table8 Thrombolytic Therapy Information After Admission and Before Thrombectomy

Item	Indicator	Experimental Group	Control Group	Total
Whether intravenous thrombolysis administered onset of symptoms and prior to mechanical thrombectomy	No n(%)			
	Yes n(%)			
	Total (Missing)			
	Statistical measure			
	P-value			

6.2.3. Screening Period Check

Table9 Screening Period Vital Signs

Item	Indicator	Experimental Group	Control Group	Total
Systolic Blood Pressure (mmHg)	N(Missing)			
	Mean (SD)			
	Median			
	Q1, Q3			
	Min, Max			
	Statistic			
	P-value			
Diastolic Blood	N(Missing)			

Item	Indicator	Experimental Group	Control Group	Total
Pressure (mmHg)	Mean(SD)			
	Median			
	Q1, Q3			
	Min, Max			
	Statistic			
	P-value			
Heart Rate (beats per minute)	N(Missing)			
	Mean(SD)			
	Median			
	Q1, Q3			
	Min, Max			
	Statistic			
	P-value			

Table10 Screening Period Pregnancy Checkup (Applicable to Women of Childbearing Age)

Item	Indicator	Experimental		
		Group	Control Group	Total
Serum HCG	Normal n(%)			
	Abnormal but Clinically Insignificant n(%)			
	Abnormal and Clinically Significant n(%)			
	Not tested n(%)			
	Not applicable n(%)			
	Total (Missing)			
	Statistic			
	P-value			
Urinary pregnancy test	Normal n(%)			
	Abnormal but Clinically Insignificant n(%)			
	Abnormal measurement with clinical significance n(%)			
	Not Performed n(%)			
	Not applicable n(%)			
	Total (Missing)			
	Statistic			
	P-value			

Table11 Screening period imaging examination - Subjects with time from stroke onset to femoral artery puncture ≤ 6 hours (inclusive)

Item	Indicator	Experimental		
		Group	Control Group	Total
Cranial CT or MRI	Yes n(%)			

Item	Indicator	Experimental Group	Control Group	Total
examination	No n(%)			
	Total (Missing)			
	Statistical measure			
	P-value			
Evaluation	None n(%)			
Information	Present n(%)			
	Total (Missing)			
	Statistic			
	P-value			

Table12 Screening period imaging examination - Participants with onset to femoral artery puncture exceeding 6 hours but not exceeding 24 hours (inclusive)

Item	Indicator	Experimental Group	Control Group	Total
Cranial CT or MRI examination	Yes n(%)			
	No n(%)			
	Total (Missing)			
	Statistic			
	P-value			
Evaluation Information	None n(%)			
	Present n(%)			
	Total (Missing)			
	Statistic			
	P-value			
ASPECTS Score - Anterior Circulation Occlusion	N(Missing)			
	Mean (SD)			
	Median			
	Q1, Q3			
	Min,Max			
	Statistic			
	P-value			
ASPECTS Score - Anterior Circulation Occlusion - Qualitative	<6 points n(%)			
	≥6 points n(%)			
	Total (Missing)			
	Statistic			
	P-value			
ASPECTS Score - Post-Circulation Occlusion	N(Missing)			
	Mean (SD)			
	Median			
	Q1, Q3			

Item	Indicator	Experimental		
		Group	Control Group	Total
ASPECTS Score - Post-Circulation Occlusion - Qualitative	Min,Max			
	Statistic			
	P-value			
	<6 points n(%)			
	≥6 points n(%)			
	Total (Missing)			
	Statistic			
	P-value			
	N(Missing)			
	Mean (SD)			
ASPECTS Score - Anterior Circulation Occlusion (CTP or MRP-assisted assessment)	Median			
	Q1, Q3			
	Min,Max			
	Statistic			
	P-value			
	<6 points n(%)			
	≥6 points n(%)			
	Total (Missing)			
	Statistic			
	P-value			
ASPECTS Score - Post-occlusion (CTP or MRP-assisted assessment)	N(Missing)			
	Mean(SD)			
	Median			
	Q1, Q3			
	Min,Max			
	Statistic			
	P-value			
	<6 points n(%)			
	≥6 points n(%)			
	Total (Missing)			
ASPECTS score - posterior circulation occlusion (CTP or MRP-assisted assessment) - qualitative	Statistic			
	P-value			

Table13 Screening Period Angiography Data

Item	Indicator	Experimental		
		Group	Control Group	Total
Normal Vessel Diameter Proximal to Target Lesion (mm)	N(Missing)			
	Mean(SD)			
	Median			
	Q1, Q3			

Item	Indicator	Experimental		Total
		Group	Control Group	
Pre-thrombectomy classification of the responsible vessel	Min,Max			
	Statistic			
	P-value			
	mTICI Grade 0 n(%)			
	Grade 1 n(%)			
	Grade 2a n(%)			
	Grade 2b n(%)			
	Grade 3 n(%)			
	Total (Missing)			
	Statistic (CMH)			
Location of Primary Culprit Vessel Before Thrombectomy - ICA	P-value			
	Yes n(%)			
	No n(%)			
	Total (Missing)			
Location of the primary responsible vessel before thrombectomy - MCA	Statistic (CMH)			
	P-value			
	Yes n(%)			
	No n(%)			
Location of the primary responsible vessel prior to thrombectomy - V4	Total (Missing)			
	Statistic (CMH)			
	P-value			
	Yes n(%)			
Location of the primary culprit vessel before thrombectomy - BA	No n(%)			
	Total (Missing)			
	Statistic (CMH)			
	P-value			

